## 6.12 VULVAR HPV TESTING

At Screening, Weeks 48, 74, and 96, a vulvar punch biopsy sample of approximately 4 mm will be obtained and sent to a central laboratory for HPV genotyping by PCR. In the case of multifocal disease, a vulvar biopsy of approximately 4 mm will be obtained from two lesions that potentially contain the most advanced disease as judged by the Investigator. The subject will be requested to abstain from sexual activity and refrain from use of douching to eliminate potential interference with the results of HPV testing.

The subject will be requested to abstain from sexual activity and refrain from use of douching or vaginal lubricants/medication for a period of 24 hours prior to collection of vulvar punch biopsy to eliminate potential interference with the results of HPV testing.

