4. Determine the efficacy of four doses of VGX-3100 , alone or in combination with imiquimod, as measured by histologic regression of vulvar HSIL to normal tissue	4. Proportion of subjects with no evidence of vulvar HSIL, no evidence of LSIL (VIN1), and no evidence of condyloma on histology (i.e. biopsies or excisional treatment) at the Week 48 visit
5. Determine the efficacy of four doses of VGX-3100 , alone or in combination with imiquimod, as measured by non-progression of vulvar HSIL to vulvar cancer as determined by histology	5. Proportion of subjects with no progression  of vulvar HSIL to vulvar cancer from baseline to Week 48 visit
6. Determine the efficacy of VGX-3100, alone or in combination with imiquimod, as measured by reduction in the surface area of qualifying vulvar lesion(s)	6. Percent reduction in the cumulative surface area of the acetowhite vulvar lesion(s) as determined by the quantitative analysis of standardized pre-biopsy photographic imaging of qualifying  lesion(s) at Week 48, 74 and 96 compared to baseline  . Results will be classified as: no clinically significant lesion resolution (reduction in lesion area of 0-25%), partial lesion area resolution (>25% and <100% reduction) and complete lesion resolution (no visible lesion).

 No evidence of vulvar HSIL is defined as normal tissue or vulvar LSIL (VIN 1) or condyloma

 Clearance of HPV-16 or HPV-18 is defined as being undetectable by PCR assay.

 Progression is defined as advancement to carcinoma by histology according to the Pathology Adjudication Committee.

 A qualifying lesion is defined as a vulvar lesion which is confirmed to be HPV-16 and/or HPV-18 positive and have histologically confirmed vulvar HSIL by the PAC at screening.

 Baseline photographic imaging is defined as photographs obtained at Day 0 prior to the first study dose. Digital photos will be analyzed with a computer program to calculate the total lesion size in cm^2.

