**Figure 1: Study Visit Schedule**

**Imiquimod treatment** - Subjects randomized to the VGX-3100 with imiquimod arm will apply imiquimod 5% cream to the vulvar lesion(s) beginning in the evening on Day 0, and will continue to apply imiquimod cream three times per week for 20 weeks (inclusive of administration in the evening of VGX-3100 dosing). Subjects unable to tolerate imiquimod treatment may reduce their dosing frequency, and will document their use on the imiquimod dosing log provided.

[figure not shown]
**Efficacy Assessment:** Biopsies obtained as part of the study at Screening will be from the region of most advanced disease as judged by the Investigator, and must be approximately 4 mm in length. Visible lesion must remain after screening biopsy to ensure measurement on study.

Visualization of a normal appearing vulva by vulvoscopy is insufficient evidence to confirm disease regression. Disease regression will be based on histopathologic assessment at Week 48, 74, and 96. Subjects will be monitored during the course of the study by vulvoscopy. Lesion(s), defined as areas that stain acetowhite, will be assessed during vulvoscopy at Screening, Day 0 and Weeks 4, 12, 27, 48, 74 and 96. Using standardized high resolution digital photographic imaging, vulvar lesion(s) will also be quantitatively measured at Screening, Day 0, and Weeks 4, 12, 27, 48, 74 and 96.

The decision process following results of the Week 48 biopsy are described in [Figure 2](#) below and as follows: At Week 48, the subject will undergo repeat vulvar punch biopsy/biopsies of the same lesion as study start, but from the region of potentially most advanced disease based upon the judgment of the Investigator (see [Table 2](#) for Minimally Required Biopsy Procedures). If after evaluation of biopsy tissue by the PAC there is no evidence of HSIL (Subgroups A or B), the subject will continue to Week 74 for vulvoscopy, and biopsy of the same lesion as study start.

[figure not shown]

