**Study Population:**

Inclusion:

1. Must understand, agree and be able to comply with the requirements of the protocol. Subjects must be willing and able to provide voluntary consent to participate and sign a Consent Form prior to study-related activities;
2. Women aged 18 and above
3. Vulvar infection with HPV types 16 and/or 18 confirmed by screening biopsy;
4. Vulvar tissue specimen/blocks must be collected within 10 weeks prior to anticipated date of first dose of study drug and have histologically confirmed vulvar HSIL by the Pathology Adjudication Committee at screening;
5. Must be judged by the Investigator to be an appropriate candidate for the protocol-specified procedure (i.e. excision or biopsy) required at Week 48;
6. Must have vulvar HSIL that is accessible for sampling by biopsy instrument and of adequate size to ensure that a visible lesion remains after an approximately 4 mm screening biopsy;
7. Must have vulvar HSIL that can be completely demarcated for area measurement;
8. Must meet one of the following criteria with respect to their reproductive capacity:
  - a) Is post-menopausal as defined by spontaneous amenorrhea for more than 12 months or spontaneous amenorrhea for 6-12 months with FSH level >40 mIU/mL;
  - b) Is surgically sterile due to absence of ovaries or due to a bilateral tubal ligation/occlusion performed more than 3 months prior to screening;
  - c) Women of Child Bearing Potential (WOCBP) are willing to use a contraceptive method with failure rate of less than 1% per year when used consistently and correctly from screening until 6 months following the last dose of investigational product. Acceptable methods are the following:
    - i) Hormonal contraception: either combined or progestin-alone including oral contraceptives, injectable, implants, vaginal ring, or percutaneous patches. Hormonal contraceptives must not be used in subjects with a history of hypercoagulability (e.g., deep vein thrombosis, pulmonary embolism);
    - ii) Abstinence from penile-vaginal intercourse when this is the subject's preferred and usual lifestyle;
    - iii) Intrauterine device or intrauterine system;
    - iv) Male partner sterilization at least 6 months prior to the female subject's entry into the study, and this male is the sole partner for that subject.
9. Has normal screening electrocardiogram (ECG) or screening ECG with no clinically significant findings as judged by the Investigator.

Exclusion:

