- c Screening 12-lead ECG, complete blood count (CBC), serum electrolytes, blood urea nitrogen (BUN), creatinine (Cr), glucose, ALT, CPK and urinalysis performed within 45 days prior to first dose administration.
- d Negative spot urine pregnancy test is required at screening and prior to each study treatment, vulvoscopy and biopsy/surgical excision.
- e At least 34 mL (4 x 8.5 mL yellow (ACD) tubes) whole blood and 4 mL serum per time point. At least 68 mL whole blood and 8 mL serum should be collected prior to first dose. One additional 8.5 mL yellow (ACD) tube to be collected at Day 0, Week 15 and 48 for microRNA analysis.
- f At least 51 mL [6 x 8.5 mL yellow (ACD) tubes] whole blood and 4 mL serum should be collected at Week 27.
- g HLA testing will be performed once from an existing PBMC sample.
- h HPV genotyping and Pap smears are performed on the same ThinPrep® cervical specimen.
- i An additional visit may be scheduled to perform vulvoscopy if worsening of disease is suspected. Biopsies should not be performed at any visit other than at entry (Screening), Week 48, and Weeks 74 and 96 for Subgroups C and D unless the Investigator suspects invasive cancer. All biopsy samples and/or excision samples must be sent to the PAC for review.
- j Photography of the acetowhite stained qualifying lesion(s) must be performed prior to and after biopsy, and at all vulvoscopy examinations. If a pre-biopsy digital photograph is not available for a historical biopsy sample at screening, a post biopsy photo will be sufficient. Additionally, standardized high resolution digital photographic imaging should be obtained during examinations of the vagina if lesions are identified, for documentation.
- k Tissue specimen from all excised tissue must be reviewed by the PAC and residual vulvar tissue from entry, Week 48, 74 or Week 96 specimen(s) (paraffin blocks or unstained slides) must be sent to the central pathology laboratory for HPV testing.
- l HPV genotyping is performed on vulvar tissue specimen using a PCR based assay.
- m Potential dosing at Week 52 and Week 78 is applicable for partial responders only.
- n Subjects will take home imiquimod plus an imiquimod dosing log to document their use of imiquimod. Administration of imiquimod begins on Day 0.

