## 2.2 SECONDARY OBJECTIVES AND ASSOCIATED ENDPOINTS

Secondary Objectives	Associated Secondary Endpoints
1. Evaluate the safety and tolerability of VGX-3100 delivered IM followed by EP with CELLECTRA™ 2000, alone or in combination with imiquimod	1a. Local and systemic events for 7 days following each dose as noted in the Participant Diary. 1b. All adverse events including SAEs, SUSARs, UADEs, and other unexpected AEs for the duration of the study (through Week 100 visit)
2. Determine the efficacy of four doses of VGX-3100, alone or in combination with imiquimod, as measured by histologic regression of vulvar HSIL	2. Proportion of subjects with no evidence of vulvar HSIL on histology (i.e. biopsies or excisional treatment) at Week 48 visit
3. Determine the efficacy of four doses of VGX-3100, alone or in combination with imiquimod, as measured by virologic clearance of HPV-16/18 in vulvar tissue	3. Proportion of subjects with no evidence of HPV-16/18 in vulvar tissue samples at Week 48 visit
4. Determine the efficacy of VGX-3100 , alone or in combination with imiquimod, as measured by histologic regression of vulvar HSIL to normal tissue	4. Proportion of subjects with no evidence of vulvar HSIL, no evidence of vulvar LSIL (VIN1), and no evidence of condyloma on histology (i.e. biopsies or excisional treatment) at the Week 48 visit
5. Determine the efficacy of four doses of VGX-3100 , alone or in combination with imiquimod, as measured by non-progression of vulvar HSIL to vulvar cancer as determined by histology	5. Proportion of subjects with no progression of vulvar HSIL to vulvar cancer from baseline to Week 48 visit
6. Determine the efficacy of VGX-3100, alone or in combination with imiquimod, as measured by reduction in the surface area of the qualifying vulvar lesion(s)	6. Percent reduction in the cumulative surface area of the acetowhite vulvar lesion(s) as determined by the quantitative analysis of standardized pre-biopsy photographic imaging of the qualifying  lesion (s) at Week 48, 74 and 96 compared to baseline  . Results will be classified as: no clinically significant lesion resolution (reduction in lesion size of 0-25%), partial lesion area resolution (>25% and <100% reduction), and complete lesion resolution (no visible lesion).

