### 3. STUDY DESIGN

HPV-201 is a Phase 2, randomized, open-label efficacy study of VGX-3100 (DNA plasmids encoding E6 and E7 proteins of HPV types 16 and 18) administered by IM injection followed by EP delivered with CELLECTRA™ 2000 alone or in combination with imiquimod in adult women with histologically confirmed vulvar HSIL associated with HPV-16/18. Approximately 36 subjects will be enrolled. Twenty-four subjects will receive VGX-3100 alone and 12 subjects will receive VGX-3100 and topical imiquimod treatment.

Subjects are randomized in a stratified manner according to (a) recurrent disease at screening (0 vs. 1 or more recurrences), (b) multifocal disease (1 vs. 2 or more lesions at screening), (c) Body Mass Index (BMI) category ( $\leq 25$  vs.  $> 25$  kg/m^2), and (d) age category ( $< 45$  years vs.  $\geq 45$  years).

To be eligible for the study, subjects must sign consent to participate and have a vulvar punch biopsy/biopsies of approximately 4 mm with lesion remaining, and photographs of the acetowhite vulvar lesion(s) at the time of screening. In the case of multifocal disease, the two lesions that potentially contain the most advanced disease, as judged by the Investigator, should be chosen for biopsy using vulvoscopy and documented using standardized high resolution photography with a digital single-lens reflex (SLR) camera on the case report form. Biopsy slides will be sent to a PAC for evaluation prior to enrollment. In order to be eligible for enrollment, the PAC must assign the diagnosis of vulvar HSIL based on the biopsy sample(s). Subjects must also have a vulvar specimen test positive for HPV genotype 16 and/or 18 to be eligible for participation in the study.

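### Lesion area at Weeks 74 and 96 is compared with Day 0 with no allowance for lesion cut out by the study's own earlier punch biopsies, which can inflate the reported reduction when lesions are small

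*Protocol*

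**What the plan says.** Section 2.2, endpoint 6, defines the percent reduction in cumulative acetowhite area "as determined by the quantitative analysis of standardized pre-biopsy photographic imaging of the qualifying" "lesion (s) at Week 48, 74 and 96 compared to baseline". Exploratory endpoint 1 in Section 2.3 uses the same measure at Weeks 74 and/or 96, in women without complete resolution at Week 48. A synopsis footnote fixes the reference: "Baseline photographic imaging is defined as photographs obtained at Day 0 prior to the first study dose". Results fall into three classes: 0 to 25% reduction, more than 25% but less than 100%, and no visible lesion.

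The synopsis also says "At Week 48, the subject will undergo repeat vulvar punch biopsy/biopsies of the same lesion as study start", and it repeats the biopsy of that lesion at Week 74. Section 6.12 (Version 2.0) gives the size: "a vulvar punch biopsy sample of approximately 4 mm will be obtained". Table 1, footnote j, requires images on both sides of each biopsy: "Photography of the acetowhite stained qualifying lesion(s) must be performed prior to and after biopsy". Entry sets no minimum area in cm2. The lesion need only be of "adequate size to ensure that a visible lesion remains after an approximately 4 mm screening biopsy".

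Section 8.9 (Version 2.0) takes the mean percent change with a t-based interval, and the class percentages with Clopper-Pearson intervals. The Version 2.1 text available breaks off in Section 3, so Sections 6.12 and 8.9 and Table 2 are cited here from Version 2.0. No text shown subtracts previously biopsied area or resets the baseline.

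**The concern.** Measuring before the biopsy, against a Day 0 image taken after the screening punch, keeps two removals out of the comparison: the screening punch and the punch of the same visit. At Week 48 that is enough. The Week 74 image, however, follows the Week 48 punch of the measured lesion, and the Week 96 image follows up to two punches. Lesion cut out at those visits is missing from the follow-up area but still present in the Day 0 area, so it can count as reduction.

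At stake are two of the three time points of a named secondary endpoint, and all of exploratory endpoint 1, which describes what happens around the optional fifth and sixth doses. A confidence interval does not show this kind of error.

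**Working it through.** The protocol states no lesion area and no allowance for biopsied tissue, so there is no figure of its own to reproduce. The check is a geometric bound.

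**Inputs**
- Punch of about 4 mm (Sections 3 and 6.12), taken as a circular diameter (assumption): a = π × (0.2 cm)² = 0.1257 cm2.
- Earlier post-baseline punches per lesion: k = 1 before Week 74 and k = 2 before Week 96 (synopsis).
- Class boundary: more than 25% (endpoint 6).
- Day 0 area A0: not given, so shown over a range.

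**No true change, no refill of the later punch sites, one qualifying lesion**

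Apparent reduction = k × a / A0, capped at 100%.

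| A0 (cm2) | Week 74 | Week 96 |
|---|---|---|
| 0.25 | 50.3% | 100% |
| 0.5 | 25.1% | 50.3% |
| 1 | 12.6% | 25.1% |
| 2 | 6.3% | 12.6% |
| 5 | 2.5% | 5.0% |
| 10 | 1.3% | 2.5% |

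The 25% line is crossed when A0 < k × a / 0.25:
- Week 74: 0.1257 / 0.25 = 0.50 cm2 (a round lesion of 8 mm).
- Week 96: 0.2513 / 0.25 = 1.01 cm2 (11.3 mm).

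**Sensitivity of those cut-offs**
- Punch diameter from 3 to 6 mm: 0.28 to 1.13 cm2 at Week 74, and 0.57 to 2.26 cm2 at Week 96.
- Two qualifying lesions, each punched: the cut-offs on cumulative area double, to 1.01 and 2.01 cm2.
- Half of each later site refills: they halve, to 0.25 and 0.50 cm2.
- All sites half refill, with the screening site still empty at Day 0: the net change at Week 74 is +0.5a − 0.5a = 0, so there is no bias. At Week 96 it is +0.5a − 2 × 0.5a = −0.5a, a cut-off of 0.5 × 0.1257 / 0.25 = 0.25 cm2.
- Later sites refill fully: no inflation.

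**Residual removed whole**

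This case does not depend on A0. Suppose a 5 cm2 lesion has shrunk by Week 48 to a residual that fits inside one punch (0.126 cm2). It is partial at Week 48: 1 − 0.126/5 = 97.5%. If the biopsy takes all of it and nothing regrows, Week 74 shows no visible lesion and the class becomes complete. The mean moves by 2.5 points but the class changes. Because exploratory endpoint 1 selects women not yet complete at Week 48, the change falls in the extended-dosing period.

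**The case against.** The strongest reply is that the effect rests on something the protocol never states: that a punched site stays free of acetowhite lesion about 26 weeks later. The background describes a persistent, HPV-driven disease with high recurrence, and a punch inside a lesion leaves lesion at its edge. Refill of the screening site after Day 0 counts as growth and offsets later punches. If every site refills fully, the error runs against the drug. This stands, and it is why the bound is a maximum.

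A reader might infer that every woman biopsied is affected. The documents do not support that. Table 2 (Version 2.0) requires a biopsy even when no acetowhite lesion is seen, and such a punch removes no measured area. Table 1, footnote i, limits Week 74 and 96 biopsies to Subgroups C and D, while the synopsis also biopsies A and B; these passages must be reconciled before the affected group is known. Women treated surgically after Week 48 have no further biopsy, so the two-punch figures do not apply to them.

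The consequence is also limited. Section 8.9 plans no tests for the secondary binary endpoints, lesion area is summarised by estimates and intervals, and both arms follow the same biopsy schedule.

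It can also be said that handling of biopsy sites belongs in an SAP or imaging manual, and those, like Section 8.9 of Version 2.1, are not shown. That would answer an unspecified detail. Here the endpoint text itself fixes the image and the baseline, and applied as written that rule counts unreplaced biopsied lesion as reduction.

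**Conclusion.** The point holds as a conditional one. As written, the Week 74 and Week 96 results can overstate lesion reduction by up to 0.126 and 0.251 cm2 per lesion. With no true change, one qualifying lesion crosses into the partial class only below about 0.50 and 1.01 cm2 at Day 0. Those cut-offs halve if half of each later site refills, and are smaller still if the screening site also refills after Day 0. For unchanged lesions above about 2.5 cm2 (Week 74) or 5 cm2 (Week 96) the inflation is 5 points or less. The complete class is exposed at any Day 0 size when a small Week 48 residual is removed whole.

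This assumes a circular 4 mm punch lying wholly in acetowhite lesion. Lesion sizes and refill rates are not given, so the share of women affected is unknown. Small lesions are eligible, and the summary of changes says the biopsy size rule was relaxed to admit smaller ones.

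A reader might go further and conclude that the area results are always biased toward benefit, or that the main efficacy result is compromised. Neither follows: refill can cancel or reverse the effect, and scheduled punches do not touch the primary endpoint or any Week 48 area result.

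**What to change.** In endpoint 6, exploratory endpoint 1 and Section 8.9, add one specified biopsy-corrected analysis for Weeks 74 and 96, using the photographs footnote j already requires:

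- For each earlier post-baseline punch, take the pre-biopsy minus post-biopsy acetowhite area and subtract it from the Day 0 area. Recompute the percent change and the class. For example, with Day 0 = 1.000, Week 48 before and after biopsy = 0.500 and 0.374, and Week 74 = 0.200 cm2, the uncorrected reduction is 80.0% and the corrected one is 1 − 0.200 / (1.000 − 0.126) = 77.1%.
- Report it beside the uncorrected result. For an otherwise unchanged lesion, and leaving the screening site aside, the two correspond to no refill and full refill of the later punch sites. The corrected value alone would over-correct if sites refill.
- If an earlier study biopsy left no visible lesion on the post-biopsy photograph, do not count the lesion as complete on drug effect at Week 74 or 96. Report those women separately, along with any whose corrected Day 0 area is zero or less.

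A chained product of visit-to-visit ratios is not a substitute. In the same example it gives 1 − (0.500/1.000) × (0.200/0.374) = 73.3%, and it is undefined when the post-biopsy area is zero.

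The cost is some extra image measurement, a sentence or two in three places, and a slightly less favourable reported reduction.

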## 2.3 EXPLORATORY OBJECTIVES AND ASSOCIATED ENDPOINTS

Exploratory Objectives	Associated Exploratory Endpoints
1. Describe the efficacy of VGX-3100, administered alone or in combination with imiquimod, at Week 74 and/or Week 96 as measured by reduction in the surface area of the qualifying  vulvar lesion(s), in subjects without a complete resolution at Week 48	1. Percent reduction in the cumulative surface area of the acetowhite vulvar lesion(s) as determined by the quantitative analysis of standardized pre-biopsy photographic imaging of the qualifying  lesion (s) at Week 74 and/or Week 96 compared to baseline  . Results will be classified as: no clinically significant lesion resolution (reduction in lesion area of 0-25%), partial lesion area resolution (>25% and <100% reduction), and complete lesion resolution (no visible lesion).
2. Describe the efficacy of 5 or 6 doses of VGX-3100, alone or in combination with prior imiquimod, as measured by histologic regression of vulvar HSIL	2. Proportion of subjects with no evidence of vulvar HSIL on histology (i.e. biopsies or excisional treatment) at Week 74 for subjects who receive 5 doses of VGX-3100 and at Week 96 for subjects who receive 6 doses of VGX-3100.
3. Describe the efficacy of 5 or 6 doses of VGX-3100, alone or in combination with prior imiquimod, as measured by virologic clearance of HPV-16/18	3. Proportion of subjects with no evidence of HPV-16/18 in vulvar tissue samples at Week 74 and/or Week 96.
4. Evaluate tissue immune responses to VGX-3100, and VGX-3100 with imiquimod, as measured in vulvar tissue samples	4. Assessment of pro-inflammatory and immunosuppressive elements in tissue 
5. Describe virologic clearance of HPV-16/18 from non-vulvar anatomic locations	5. Proportion of subjects who have cleared HPV-16/18 on specimens from non-vulvar anatomic locations without surgical intervention (inclusive of cervix, oropharynx, vagina and intra-anus) at Week 48 compared to baseline
6. Characterize HLA haplotypes and the correlation with efficacy	6. Proportion of subjects with regression of HSIL on histology (i.e. biopsies or excisional treatment) at Week 48 visit
7. Describe association of microRNA (miRNA) profile, previous vulvoscopy, and HPV testing results with Week 48 histologic regression	7. Vulvoscopy, HPV test results (vulvar swab and vulvar tissue) and miRNA profile (Day 0, Week 15 and 48) in conjunction with histologic regression of vulvar HSIL at Week 48 visit
8. Describe patient reported outcomes (PRO) for subjects treated with VGX-3100 and VGX-3100 with imiquimod	8. PRO endpoints will be obtained at Day 0 prior to first dose, Weeks 4, 12, 24 after dosing, and at Weeks 15, 27, 48, 52, 74, 96 and 100.

